4.0 PATIENT ELIGIBILITY AND INELIGIBILITY

4.1 Conditions for patient eligibility

A patient cannot be considered eligible for this study unless all of the following conditions are met:

- 4.1.1 The patient must have consented to participate and, prior to beginning specific study procedures, must have signed and dated an appropriate IRB-approved consent form that conforms to federal and institutional guidelines for study treatment and for submission of tumor and blood samples as required by FC-9 correlative science studies (see [Section 6.0](#)).
- 4.1.2 Patients must be ≥ 18 years old.
- 4.1.3 The ECOG performance status must be 0 or 1 (see [Appendix A](#)).
- 4.1.4 There must be histologic confirmation of a diagnosis of colorectal adenocarcinoma.
- 4.1.5 The tumor must have been determined to be microsatellite stable (MSS).
- 4.1.6 There must be documentation by PET/CT scan, CT scan, or MRI, that the patient has evidence of measurable metastatic disease per RECIST 1.1.
- 4.1.7 Patients must have an accessible metastatic lesion for pretreatment core biopsy.
- 4.1.8 Unless either drug is medically contraindicated, patients must have received oxaliplatin and irinotecan as part of standard metastatic chemotherapy regimens.
- 4.1.9 The patient must have multiple sites of metastatic disease with at least one lesion amenable to treatment with stereotactic radiation therapy (SBRT) in the lung or liver and at least one lesion not being irradiated and meeting RECIST 1.1. (See [Appendix B](#)).
- 4.1.10 At the time of study entry, blood counts performed within 2 weeks prior to study entry must meet the following criteria:
 - ANC must be $\geq 1500/\text{mm}^3$,
 - Platelet count must be $\geq 100,000/\text{mm}^3$; and
 - Hemoglobin must be ≥ 9 g/dL.
- 4.1.11 The following criteria for evidence of adequate hepatic function performed within 2 weeks prior to study entry must be met:
 - Total bilirubin must be $\leq 1.5 \times \text{ULN}$ (upper limit of normal) for the lab unless the patient has a bilirubin elevation $> 1.5 \times \text{ULN}$ to $3 \times \text{ULN}$ due to Gilbert's disease or similar syndrome involving slow conjugation of bilirubin; *and*
 - AST and ALT must be $\leq 2.5 \times \text{ULN}$ for the lab *with the following exception*: for patients with documented liver metastases, AST and ALT must be $\leq 5 \times \text{ULN}$.

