8.0 TREATMENT MANAGEMENT

8.1 General instructions

- The NCI CTCAE v4.0 must be used to grade the severity of AEs.
- All treatment decision must be based on the AE requiring the greatest modification.
- Drug doses that have been reduced may not be re-escalated.
- All hematologic, gastrointestinal, and genitourinary toxicities must be < Grade 2 prior to initiating Dose 1 of study therapy. Patients unable to receive Dose 1 will be considered screen failures.

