Gastrointestinal disorders			
Diarrhea/Enterocolitis (See Sections 8.5.1 and 8.5.4 .)	1	Maintain study dose schedule without delay; adjust antidiarrheal medication.	
	2	Hold study therapy and adjust antidiarrheal medication. Once event is stabilized to ≤ Grade 1 after completion of the steroid taper, then resume: ↓ one dose level. If steroid taper completion is > 28 days: Discontinue further study therapy.	
	3	Hold study therapy and adjust antidiarrheal medication. If event is stabilized to ≤ Grade 1 within 14 days, after completion of the steroid taper, resume: ↓ one dose level. If there is no improvement within 14 days or steroid taper completion is > 28 days: Discontinue further study therapy.	
	4	Discontinue study therapy	
Hepatobiliary Disorders			
Hepatitis/hepatotoxicity (See Sections 8.5.5 , 8.6.2 , and 8.7 .)	3, 4	Discontinue study therapy	

Table 7 continued on next page.

Table 7. Treatment management for study therapy (continued)

CTCAE v4.0 Adverse Event	CTCAE v4.0 Grade	Action to be Taken with Study Therapy	
		Tremelimumab	Durvalumab
Immune System Disorders			
Allergic reaction/ Infusion reaction (See Table 4 and Sections 8.5.1 and 8.5.2 .)	1	The infusion rate of study therapy may be decreased by 50% or temporarily interrupted until resolution of the event. Maintain study dose level.	
	2	The infusion rate of study therapy may be decreased 50% or temporarily interrupted until resolution of the event. Subsequent infusions may be given at 50% of the initial infusion rate. Once event is stabilized to ≤ Grade 1, after completion of the steroid taper, resume: ↓ one dose level. If steroid taper completion is > 28 days: Discontinue further study therapy.	
	3,4	Discontinue study therapy	
Investigations			
Immune-mediated hepatitis as indicated by: 
 • Alanine transferase (ALT) increased • Alkaline phosphatase increased • Aspartate aminotransferase (AST) increased • Blood bilirubin increased Note: Permanently discontinue study therapy for any case meeting Hy's Law criteria. (See Sections 8.5.5 , 8.6.2 , and 8.7 [Hy's Law].)	1	Monitor LFTs; Maintain study dose level.	

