	2	Note: For patients with metastatic liver disease who enter the study with Grade 2 transaminases: Maintain dose and continue study therapy without holding. Otherwise: Hold study therapy. Once elevations have resolved to ≤ Grade 1 and, 
 • No systemic steroid therapy has been initiated then resume: Maintain dose level • Systemic steroid therapy has been initiated – after completion of the steroid taper, resume: ↓ one dose level or discontinue. • If steroid taper completion is > 28 days: Discontinue further study therapy. 	

Table 7 continued on next page.

Table 7. Treatment management for study therapy (continued)

CTCAE v4.0 Adverse Event	CTCAE v4.0 Grade	Action to be Taken with Study Therapy	
		Tremelimumab	Durvalumab
Investigations (continued)			
Immune-mediated hepatitis as indicated by: 
 • Alanine transferase (ALT) increased • Alkaline phosphatase increased • Aspartate aminotransferase (AST) increased • Blood bilirubin increased Note: Permanently discontinue study therapy for any case meeting Hy's Law criteria. (See Sections 8.5.5, 8.6.2, and 8.7 [Hy's Law].)	3	Elevations in transaminases $\leq 8 \times$ ULN and bilirubin $\leq 5 \times$ ULN: Hold study therapy; if elevations resolve to \leq Grade 1 or base line within 14 days , and if 
 • no systemic steroid therapy has been initiated: then resume: Maintain dose or \downarrow one dose level. • systemic steroid therapy has been initiated – after completion of the steroid taper, resume: \downarrow one dose level or discontinue. • If steroid taper completion is > 28 days: discontinue. Note: If elevations do not downgrade to \leq Grade 1 within 14 days OR for elevations in transaminases $> 8 \times$ ULN or bilirubin $> 5 \times$ ULN: Discontinue further study therapy. Discontinue study therapy for any case meeting Hy's law criteria and in the absence of any alternative cause. 	
	4	Discontinue study therapy	
Creatinine increased (Nephritis) (See Sections 8.5.1 and 8.5.6.)	1	Maintain study dose level	
	2	Hold study therapy until resolved to \leq Grade 1 after completion of the steroid taper, resume: \downarrow one dose level. If steroid taper completion is > 28 days: Discontinue further study therapy.	
	3, 4	Discontinue study therapy	

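### For the same Grade 3 liver-test elevation, one Table 7 row requires discontinuation and another allows hold-and-resume; the Grade 3 Note also omits return to baseline

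*Combined protocol and SAP*

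**What the plan says.** Table 7 (protocol Section 8.4) has two liver entries.

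- **Hepatobiliary Disorders.** The row labelled "Hepatitis/hepatotoxicity (See Sections 8.5.5" covers Grades 3 and 4 with one action, discontinue. It gives no laboratory limit.
- **Investigations.** The row headed "Immune-mediated hepatitis as indicated by" lists increases in ALT, alkaline phosphatase, AST and bilirubin. At Grade 3, with transaminases at most 8 × ULN and bilirubin at most 5 × ULN, the order begins "Hold study therapy; if elevations resolve to" and accepts Grade 1 or below, or baseline, within 14 days. If no systemic steroid was started, dosing resumes at the same level or one level down. If steroids were started, the choice after the taper is one level down or discontinue, and a taper longer than 28 days means stopping. A Note closing the cell orders discontinuation if values have not come down to "Grade 1 within 14 days OR for elevations in transaminases" above 8 × ULN or bilirubin above 5 × ULN.

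Both rows cite Sections 8.5.5, 8.6.2 and 8.7. Section 8.5.5 has the title of the first row, explains it as elevation of AST, ALT, ALP and total bilirubin, and gives a hold-and-resume rule at Grade 3. It accepts baseline in both its resume rule and its stop rule, and it sends the reader back to Table 7 for dosing.

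On baseline values, 4.1.11 has an exception: "for patients with documented liver metastases, AST and ALT must be" no more than 5 × ULN. The Grade 2 Investigations cell makes separate provision for "patients with metastatic liver disease who enter the study with Grade 2 transaminases".

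**The concern.** Two sites can see the same laboratory event, each follow a row of Table 7, and act differently. One stops both drugs permanently, since 8.3 discontinues them together. The other holds and re-treats. So a patient may be re-treated although one row says stop, or lose therapy that another row allows.

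The event is foreseeable. Every patient receives SBRT to a lung or liver lesion. Section 8.6.2 expects transient enzyme rises after treatment of liver or right-lower-lobe lesions and gives monitoring advice for rises up to Grade 3.

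The SAP tabulates AEs leading to permanent discontinuation (6.2) and the number of started cycles (6.1), so both summaries can depend on which row a site read.

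**Working it through.** The plan states no figure to reproduce here. The check is a comparison of texts followed by simple arithmetic.

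**Step 1. Compare the orders case by case.** In this table the limits are transaminases ≤ 8 × ULN and bilirubin ≤ 5 × ULN.

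| Event | Hepatobiliary row | Investigations row | Section 8.5.5 | Result |
|---|---|---|---|---|
| Grade 3 AST, ALT or bilirubin within limits, not Hy's Law, recovered by day 14, no steroids | Discontinue | Resume, same dose or one level down | Resume | Opposite orders |
| Same, steroids given, taper within 28 days | Discontinue | One level down or discontinue | Resume after taper | Required versus optional |
| Isolated Grade 3 alkaline phosphatase, recovered by day 14 | Discontinue | As in the two lines above | No graded rule | Conflict within Table 7 only |
| Grade 3 within limits, neither Grade ≤ 1 nor baseline by day 14 | Discontinue | Discontinue | Discontinue | Agree |
| Grade 3 above either limit, Grade 3 Hy's Law case, or Grade 4 | Discontinue | Discontinue | Discontinue | Agree |

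Alkaline phosphatase has its own line because 8.5.5 names it in the subtitle and the monitoring sentence, while its graded rules cover only AST, ALT and total bilirubin.

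**Step 2. Look for a rule that selects the row.**

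- The cross-references do not separate the rows, because both cite the same three sections.
- The labels state no boundary. Elsewhere Table 7 does state one: the neurotoxicity row excludes myasthenia gravis and Guillain-Barre, and bullous rash has its own row.
- Section 8.1 says "All treatment decision must be based on the AE requiring the greatest modification". That ranks different AEs. Applied to two rows for one AE, it would always select discontinuation, and the Grade 3 hold cell and the 8.5.5 resume rule would never operate.

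**Step 3. Test the Note.** Take a patient with liver metastases who enters with Grade 2 transaminases, rises to Grade 3 within the limits, and is back at the Grade 2 baseline by day 14.

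- Opening order of the Grade 3 cell: resume, because baseline is reached.
- Note in the same cell: discontinue, because Grade 1 is not reached.
- Section 8.5.5: resume, because its stop rule also accepts baseline.

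If baseline is Grade 1 or below, the Note and the opening order give the same answer.

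**Step 4. Size per patient.** Suppose the event follows the Cycle 2 dose. Planned doses are 24 of durvalumab and 4 of tremelimumab (Section 7.1, Table 4).

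- Durvalumab not given if stopped: 24 − 2 = 22, and 22/24 = 91.7%.
- Tremelimumab not given if stopped: 4 − 2 = 2, and 2/4 = 50%.
- One patient's share of the discontinuation rate: 1/12 = 8.3 points at Stage I size, 1/21 = 4.8 points at full size.

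The dose counts assume that the patient would otherwise have received every remaining dose. The shares fall if replaced patients enlarge the safety denominator.

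**The case against.** The strongest reply is that a laboratory-only event already has its own row. Table 7 is arranged by CTCAE adverse event, the four liver tests are named only under Investigations, and creatinine increase is placed there too. The Hepatobiliary row names no test and starts at Grade 3, which suits clinical hepatotoxicity. The opening of 8.4 also points to 8.5 for dose changes, and 8.5.5 sides with the Investigations row. This is probably the intended split, and the fix adopts it. But Table 7 does not state it, and 8.5.5 defines the Hepatobiliary row's own title by laboratory elevation.

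A second reply concerns steroids. A reader might infer that the two rows always give opposite orders. They do not. Section 8.5.5 recommends prompt intravenous methylprednisolone at Grade 3, and once steroids are started a site that discontinues complies with both rows. Fully opposite orders arise only on the no-steroid branch, which Table 7 provides for itself. This limit stands.

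Third, the missing baseline wording is editorial and touches few patients. That is fair as to scope, but for those patients one cell still says both resume and stop.

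Fourth, 8.6.2 describes radiation-caused rises, while the Investigations row is headed as immune-mediated. This weakens the foreseeability argument without removing it, since both rows cite 8.6.2.

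Finally, AESIs of Grade 2 or above are reported within 24 hours (10.4.2, 10.7.2), and 14.3 sets a weekly call and monthly review. These can settle single cases, but they state no rule.

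**Conclusion.** Table 7 is wrong as written, in two limited ways.

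1. For a Grade 3 AST, ALT or bilirubin elevation within 8 × and 5 × ULN and not meeting Hy's Law, the Hepatobiliary row requires discontinuation while the Investigations row and 8.5.5 allow resumption on recovery within 14 days. Isolated Grade 3 alkaline phosphatase elevation has the same conflict inside Table 7 only.
2. The Grade 3 Note contradicts its own cell and 8.5.5 for patients whose baseline is above Grade 1.

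The consequence is inconsistent dosing and safety management between sites, carried into descriptive discontinuation and exposure tables. One patient shifts the discontinuation rate by at most 8.3 points (of 12) or 4.8 points (of 21).

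Two stronger readings are tempting. A reader might infer that a patient stopped by this row loses 92% of planned durvalumab. The 22 doses are a ceiling, because progression ends treatment (8.2.2) and Section 2.1 puts median survival on best supportive care at about 5 months. A reader might also infer a bias in ORR, since a patient stopped before completing Cycle 2 is non-evaluable and replaced. The documents give no rate of Grade 3 liver events for this regimen and nothing to fix a direction, so neither a frequency nor an ORR effect is supported.

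The change should be made. The textual finding itself rests on no numerical assumption.

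**What to change.** Make two edits in Table 7.

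1. **Hepatobiliary row.** Replace the single Grade 3 and 4 action with: *Grade 3 shown only by laboratory elevation (AST, ALT, alkaline phosphatase, bilirubin): follow the Grade 3 rule under Investigations in this table. Grade 3 clinical hepatotoxicity (e.g., RILD), any Hy's Law case, and Grade 4: discontinue study therapy.* The pointer goes to Table 7 rather than to 8.5.5 because 8.5.5 has no graded rule for isolated alkaline phosphatase.
2. **Grade 3 Investigations Note.** Insert *or baseline* after *≤ Grade 1*, as in 8.5.5.

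The cost is one protocol amendment with two wording changes. It adds no procedure, visit or patient, and it keeps the stop for clinical hepatotoxicity, Hy's Law cases and Grade 4.

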Grade 3 diarrhea: stool frequency of ≥ 7 over baseline per day; Grade 4 diarrhea: life threatening consequences. Grade 3 colitis: severe abdominal pain, change in bowel habits, medical intervention indicated, peritoneal signs; Grade 4 colitis: life-threatening consequences, urgent intervention indicated.
 - Permanently discontinue study therapy for Grade 3 if toxicity does not improve to Grade ≤ 1 within 14 days; study therapy can be resumed after completion of steroid taper.
 - Discontinue study therapy for Grade 4.
 - Promptly initiate empiric IV methylprednisolone 2 to 4 mg/kg/day or equivalent.
 - Monitor stool frequency and volume and maintain hydration.
 - Urgent GI consult and imaging and/or colonoscopy as appropriate.
 - Report event to DSSM.
 - If still no improvement within 3-5 days of IV methylprednisolone 2 to 4mg/kg/day or equivalent, promptly start further immunosuppressives (e.g. infliximab at 5 mg/kg once every 2 weeks).
 - Caution: Ensure GI consult to rule out bowel perforation and, if administered, refer to infliximab label for general guidance before using infliximab.
 - Once improving, gradually taper steroids (28 days of taper) and consider prophylactic antibiotics, antifungals and anti PJP treatment (refer to current

NCCN guidelines for treatment of cancer-related infections [Category 2B recommendation]).

8.5.5 **Hepatitis/hepatotoxicity**
(Elevation in AST, ALT, ALP and total bilirubin)

Monitor and evaluate liver function test: AST, ALT, ALP and total bilirubin (TB). Evaluate for alternative etiologies (e.g., viral hepatitis, disease progression, concomitant medications). **Infliximab should not be used for management of immune-related hepatitis.** Prompt treatment with steroids is important per guidelines below. For study treatment dose management related to imAEs, see [Section 8.5.1](#) and [Table 7](#).

- *Grade 1 AST or ALT and/or TB elevation:*
 - Continue LFT monitoring per protocol.
- *Grade 2 AST or ALT and/or TB elevation:*

Note: For patients with metastatic liver disease who enter the study with Grade 2 transaminases, maintain dose and continue study therapy without holding. Otherwise Hold study therapy.

 - Regular and frequent checking of LFTs (e.g. every 1-2 days) until elevations are improving or resolved.
 - If no resolution to \leq Grade 1 (*or baseline*) in 1-2 days, discuss with study physician. If event is persistent ($>$ 3-5 days) or worsens, promptly start prednisone 1-2 mg/kg/day PO or IV equivalent.

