 - If still no improvement within 3-5 days despite prednisone 1-2mg/kg/day PO or IV equivalent, consider additional workup and prompt treatment with IV methylprednisolone 2-4 mg/kg/day started.
 - If still no improvement within 3-5 days despite 2-4 mg/kg/day of IV methylprednisolone, promptly start immunosuppressives (mycophenolate mofetil). Discuss with study physician if mycophenolate mofetil is not available.

Infliximab should NOT be used.

 - Once improving, gradually taper steroids (28 days of taper) and consider prophylactic antibiotics, antifungals and anti PJP treatment (refer to current NCCN guidelines for treatment of cancer-related infections [Category 2B recommendation]).
 - Report event to DSSM.

Grade 3 or 4 AST or ALT and/or TB elevation:

.For Grade 3:

- For elevations in transaminases $\leq 8 \times$ ULN, or elevations in bilirubin $\leq 5 \times$ ULN:
 - Hold study therapy dose until resolution to Grade ≤ 1 or baseline.
 - Resume study therapy if elevations downgrade to Grade ≤ 1 or baseline within 14 days and after completion of steroid taper.
 - Permanently discontinue study therapy if the elevations do not downgrade to Grade ≤ 1 or baseline within 14 days.
- For elevations in transaminases $> 8 \times$ ULN or elevations in bilirubin $> 5 \times$ ULN, discontinue study therapy.
- Permanently discontinue study therapy for any case meeting Hy's law criteria (AST and/or ALT $> 3 \times$ ULN + bilirubin $> 2 \times$ ULN without initial findings of cholestasis (i.e., elevated alkaline P04) and in the absence of any alternative cause.

Grade 4

- Discontinue study therapy.

Grade 3 or 4:

- Promptly initiate empiric IV methylprednisolone at 1 to 4 mg/kg/day or equivalent.
- If still no improvement within 3-5 days despite 1 to 4 mg/kg/day methylprednisolone IV or equivalent, promptly start treatment with immunosuppressive therapy (mycophenolate mofetil). Discuss with study physician if mycophenolate mofetil is not available.

Infliximab should NOT be used.

- Obtain a Hepatology consult, abdominal workup, and imaging as appropriate.
- Once improving, gradually taper steroids (28 days of taper) and consider prophylactic antibiotics, antifungals and anti PJP treatment (refer to current NCCN guidelines for treatment of cancer-related infections [Category 2B recommendation]).
- Report event to DSSM.

8.5.6 **Nephritis**

(serum creatinine elevation)

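### Table 7 gives opposite instructions on restarting after in-limit Grade 3 hepatitis, and its Grade 1 neuromotor row conflicts with section 8.5.10

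*Combined protocol and SAP*

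**What the plan says.** **Grade 3 hepatitis.** Protocol section 8.4, Table 7, covers this event in two rows.

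- The Hepatobiliary row, labelled "Hepatitis/hepatotoxicity (See Sections 8.5.5" and also citing 8.6.2 and 8.7, ends treatment at Grades 3 and 4 without exception.
- The Investigations row is headed as immune-mediated hepatitis shown by ALT, alkaline phosphatase, AST or bilirubin, and cites the same three sections. At Grade 3, with transaminases ≤ 8 × ULN and bilirubin ≤ 5 × ULN, it says "Hold study therapy; if elevations resolve to" Grade 1 or below, or to baseline, within 14 days, treatment may restart. Without steroids the restart is at the same dose or one level lower. After steroids the choice is one level lower or stopping. A Note in the same cell, starting "If elevations do not downgrade to" and naming only Grade 1 or below, ends treatment.

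Section 8.5.5 carries the Hepatobiliary row's term and subtitles it "Elevation in AST, ALT, ALP and total bilirubin". At Grade 3 it allows a restart once values reach Grade 1 or below "or baseline within 14 days and after completion of steroid taper". Its stop clause, "Permanently discontinue study therapy if the elevations do not downgrade to Grade" 1 or below, also accepts baseline.

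**Grade 1 peripheral neuromotor syndrome.** The Table 7 row for this syndrome leaves dosing unchanged at Grade 1. Section 8.5.10 says to hold treatment and contact DSSM.

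**The concern.** These are stop-and-restart rules for immune toxicity, and a site can comply with one while breaching another. A site using the Investigations row may re-treat a Grade 3 hepatitis patient whom the Hepatobiliary row takes off treatment. A site using the neuromotor row may give the next dose to a Grade 1 patient whom 8.5.10 would hold, in a syndrome where that section warns of sudden and possibly fatal deterioration.

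The liver event is foreseeable. Section 8.6.2, cited by both hepatitis rows, expects transient enzyme rises in some patients after radiation to liver or right-lower-lobe lesions. Section 2.5 lists raised liver function tests among the most frequent events with this drug combination.

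**Working it through.** No arithmetic applies, and the plan states no figure on this point. The check sets the texts side by side.

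**Step 1: do both hepatitis rows cover the same event?** One could try to separate clinical hepatitis (Hepatobiliary) from laboratory changes (Investigations). The wording does not allow it. The Investigations row is itself headed as hepatitis, and 8.5.5 defines the Hepatobiliary row's term by the laboratory elevations. One event meets both rows.

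**Step 2: where do they disagree?**

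| Case | Hepatobiliary row | Investigations row | 8.5.5 |
|---|---|---|---|
| Grade 4 | stop | stop | stop |
| Grade 3, Hy's Law met | stop | stop | stop |
| Grade 3, above either limit | stop | stop | stop |
| Grade 3, within both limits, not resolved in 14 days | stop | stop | stop |
| Grade 3, within both limits, resolved, no steroids | stop | restart, same dose or one level lower | restart |
| Grade 3, within both limits, resolved, steroid taper within 28 days | stop | one level lower, or stop | restart after taper |

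The conflict is confined to the last two lines. Section 8.5.5 recommends prompt IV steroids for Grade 3, so the last line is the usual path. There, stopping is open under both Table 7 rows, and 8.5.5 is only recommended guidance. The dispute is therefore over whether restarting is allowed.

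**Step 3: the baseline wording.** Section 4.1.11 says that "for patients with documented liver metastases, AST and ALT must be" no more than 5 × ULN, and the Grade 2 Investigations cell expressly provides for patients with liver metastases who enter with Grade 2 transaminases. Suppose such a patient rises to Grade 3 within the limits and is back at the Grade 2 baseline by day 14.

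- Investigations restart clause: baseline reached, so restart.
- Investigations Note: not at Grade 1 or below, so stop.
- 8.5.5: baseline counts in both clauses, so restart.

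One table cell gives this patient two opposite orders.

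**Step 4: Grade 1 neuromotor syndrome.**

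| Situation | Text that applies | Action |
|---|---|---|
| Being worked up under the Neurotoxicity row | Table 7, Neurotoxicity, Grade 1 | hold |
| Guillain-Barre or myasthenia gravis confirmed | 8.2.2 | stop |
| Filed directly under the neuromotor row, not confirmed | Table 7, neuromotor, Grade 1 | dosing unchanged |
| Same patient | 8.5.10, Grade 1 | hold, contact DSSM |

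Only the last two lines conflict.

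**Step 5: is there a precedence rule?** Section 8.5 calls its guidance recommended and sends dose management to Table 7. Section 8.4 says doses can be modified as set out in 8.5 to 8.7. Neither says which prevails. If Table 7 governs, the less cautious neuromotor instruction applies, and for hepatitis the question remains, because both rows are in Table 7.

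**The case against.** **Section 8.1 could break the tie.** It bases treatment decisions on the adverse event calling for the largest modification. That ranks different events; here one event has two rules. Used here, it would mean that the Grade 3 restart branches in Table 7 and 8.5.5 could never operate.

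**The detailed rule appears twice.** The Investigations row and 8.5.5 agree with each other against one unqualified line. This is a good guide to the likely intent, and the fix follows it. It does not tell a site that the Hepatobiliary line may be disregarded.

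**Safeguards exist.** Adverse events of special interest at Grade 2 or above reach DSSM within 24 hours (10.7.2), and investigators with a patient on treatment must join a weekly call (14.3). These allow advice case by case but do not say which row is right. The 24-hour rule does not reach a non-serious Grade 1 neuromotor case, and the Grade 1 instruction to contact DSSM is in 8.5.10, the text that a Table 7 reader may bypass. Doses are 28 days apart with an assessment before each, which gives time to notice a problem but not a rule to apply.

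**Stronger readings.** A reader might infer from the *or* in 8.5.5 ("ULN, or elevations in bilirubin") that a patient above one limit may restart. The next bullet in 8.5.5 stops treatment above either limit, so this is a copy-edit. A reader might also infer that confirmed Guillain-Barre or myasthenia gravis could go on being dosed at Grade 1. Section 8.2.2 rules that out, and the Neurotoxicity row holds during work-up.

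**Conclusion.** Both contradictions stand, each in a narrow form. For hepatitis, it is whether a patient may restart after a Grade 3 event within both limits that resolves in 14 days, plus the baseline omission for patients who entered at Grade 2. For neuromotor syndrome, it is an unconfirmed Grade 1 case filed directly under that row. In each pair the two instructions cannot both be intended, so the text should be corrected.

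The frequency cannot be sized from the documents. A reader might take the 7 of 694 treatment-related Grade 3 or higher AST rises on durvalumab alone (section 2.3.2) as a ceiling. It is not one: it counts AST only, 5 ALT cases are listed separately with unknown overlap, and it involves neither tremelimumab nor SBRT. The conclusion does not depend on any rate.

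A reader might also infer damage to the response-rate analysis. The documents do not support that. The figures in section 14.2 follow from the stage sizes, the response cut-offs and the assumed response rates, and none of these is touched. The effect is on patient safety and consistent dosing between sites. The hepatitis conclusion assumes that 8.5.5's definition applies to the Hepatobiliary row, which cites it.

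**What to change.** 1. **Hepatobiliary row.** Keep the stop at Grade 4. Make Grade 3 defer to the Investigations row and 8.5.5: hold, and restart only if transaminases are ≤ 8 × ULN, bilirubin is ≤ 5 × ULN, and values return to Grade 1 or below or to baseline within 14 days. Otherwise, or if Hy's Law is met, discontinue. The existing steroid-taper conditions stay. The sponsor's safety physicians should confirm that this is the intended rule.
2. **Investigations Note.** Add the baseline alternative to the 14-day stop clause, so that it matches the restart clause and 8.5.5.
3. **Neuromotor row, Grade 1.** Change to hold during work-up, and discontinue if Guillain-Barre or myasthenia gravis is confirmed. This agrees with 8.5.10 and 8.2.2.

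The cost is amendment text. Sample size, endpoints, analyses and data collection stay as they are.

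### Table 7's Grade 3 immune-mediated hepatitis cell lets therapy restart at baseline, but its own Note stops a patient whose baseline is above Grade 1

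*Combined protocol and SAP*

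**What the plan says.** The cell at issue is in protocol section 8.4, Table 7, under Investigations: immune-mediated hepatitis, Grade 3. For transaminases up to 8 x ULN and bilirubin up to 5 x ULN, therapy is held. It may restart if values come down within 14 days to no worse than "Grade 1 or base line". Three branches follow:

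- No systemic steroids: restart at the same dose or one level lower.
- Steroids given and the taper completed: the cell offers a reduction of "one dose level or discontinue".
- Taper longer than 28 days: discontinue.

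The Note that closes the cell discontinues therapy on a test worded "Grade 1 within 14 days OR for elevations in transaminases" above 8 x ULN or bilirubin above 5 x ULN. Its 14-day test names Grade 1 only.

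Section 8.5.5 covers the same event. Its restart rule reads "or baseline within 14 days and after completion of steroid taper", and its stop rule, which begins "Permanently discontinue study therapy if the elevations do not downgrade to Grade", also goes on to name baseline as an acceptable level.

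Two places show that a baseline above Grade 1 is foreseen. Eligibility criterion 4.1.11 says that "for patients with documented liver metastases, AST and ALT must be" no more than 5 x ULN (2.5 x ULN for other patients). The Grade 2 cell of the same Table 7 row says: "For patients with metastatic liver disease who enter the study with Grade 2 transaminases: Maintain dose and continue study therapy without holding".

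**The concern.** The restart clause and the Note set different recovery targets for the same event over the same 14 days. The word baseline in the restart clause helps only patients whose starting value is above Grade 1, because for everyone else recovery to baseline already means Grade 1 or lower. Those are exactly the patients whom the Note discontinues.

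At stake is permanent loss of treatment. Section 8.3 stops durvalumab and tremelimumab together, so a patient who is back at a liver value accepted at entry could lose both drugs, although another sentence in the same cell allows restart. The site also cannot tell from the text which action complies with the protocol.

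**Working it through.** The plan gives no figure to reproduce and no arithmetic applies, so the check sets the rules side by side. Baseline is taken to mean the patient's value before study therapy.

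**1. Where the two rules overlap.** Consider a Grade 3 event within the 8 x ULN and 5 x ULN limits.

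- Restart rule (Table 7): by day 14, at Grade 1 or lower, or at baseline.
- Stop rule (Note): by day 14, not at Grade 1 or lower.

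If baseline is Grade 1 or lower, any patient at baseline is also at Grade 1 or lower. The stop rule is then the exact opposite of the restart rule, and there is no conflict. If baseline is above Grade 1, a patient who is back at baseline but still above Grade 1 meets both rules. That is the only overlap.

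**2. Whether such a patient can exist.** Yes. Criterion 4.1.11 admits AST and ALT up to 5 x ULN with liver metastases, and the Grade 2 cell names patients who enter at Grade 2. The protocol does not print the CTCAE cut-offs, but none is needed here because Table 7 itself refers to entry at Grade 2.

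**3. The overlap patient in each branch.**

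| Branch | Restart clause | Note | Result |
|---|---|---|---|
| No steroids | Same dose or one level lower | Discontinue | Opposite instructions |
| Steroids, taper 28 days or less | One level lower, or discontinue | Discontinue | Restart option removed |
| Taper over 28 days | Discontinue | Discontinue | Agree |

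Of the three branches, one is contradictory, one loses an option and one is consistent. Section 8.5.5 starts IV methylprednisolone at Grade 3, so the second branch is likely to be more usual than the first.

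**4. Comparison with section 8.5.5.** At Grade 3, that section names baseline in its hold, restart and stop rules: 3 of 3. Table 7 names it in the restart clause but not in the Note: 1 of 2.

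**5. Which text governs.** Section 8.3 places the toxicity instructions in Table 7. Section 8.5 describes its guidelines as recommended, and 8.5.5 refers dose management to 8.5.1 and Table 7. A site that follows the cross-references ends up back at the conflicting cell.

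**6. Effect of the change.** With baseline added, the Note's 14-day test becomes: neither at Grade 1 or lower nor at baseline. That is the exact opposite of the restart rule, so the overlap disappears.

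**The case against.** The strongest reply is that the protocol already shows what it means. The restart clause, the Grade 2 exception and all three Grade 3 rules in 8.5.5 point one way, and only the Note differs. Section 8.4 also says that dosing can be modified as 8.5 to 8.7 describe, and the Table 7 row cites 8.5.5. This stands as evidence of intent. It does not remove the conflict, because the recommended text gives way to Table 7 on dosing and a general pointer does not cancel a specific Note.

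A second reply is that the Note errs toward caution and that the sponsor would hear quickly. Events of special interest at Grade 2 or above are reported within 24 hours, and investigators with a patient on therapy must join a weekly call. This also stands: the cost is possible lost treatment, not unsafe re-exposure, and it is a good reason to rate the point low.

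A third reply is that section 8.1 bases decisions on the adverse event requiring the greatest modification. That rule ranks different events. It does not choose between two clauses written for one event.

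A reader might go further and infer that the separate Hepatobiliary Disorders row, which discontinues all Grade 3 hepatitis or hepatotoxicity, is a second error, particularly since 8.6.2 expects transient enzyme rises after SBRT. The documents do not establish that. The row sits under a different system heading, and its unconditional stop may be deliberate. Softening it is a clinical judgement, and stating its scope would only add detail. A rise attributed to radiation and not to an immune mechanism has its own Grade 3 hold path in Table 7's last block, on non-immune-mediated events, and that path does accept return to baseline.

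**Conclusion.** Wrong as written; minor. The Note conflicts with the restart clause of its own cell, and the slip is in an operative dosing rule.

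The affected group is narrow. A patient needs a baseline above Grade 1, an immune-mediated Grade 3 rise within the 8 x ULN and 5 x ULN limits, and return to baseline but not to Grade 1 within 14 days. Outright contradiction also requires that no steroids were used. The documents give no rate for any of these steps, so the expected number of patients cannot be derived.

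A reader might infer that every Grade 3 hepatitis case is caught, or that the trial's efficacy decision is compromised. Neither follows. Patients with a baseline of Grade 1 or lower meet only one rule. The Simon design (12 evaluable patients, then 21, with at least 3 responses needed) does not depend on this cell. A patient stopped before completing Cycle 2 would be non-evaluable and replaced under section 14.2, but nothing in the documents shows that this would happen often enough to matter.

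**What to change.** In Table 7, Investigations, immune-mediated hepatitis, Grade 3, change the opening condition of the Note to: 'If elevations do not downgrade to <= Grade 1 or baseline within 14 days'. Leave the stops for transaminases above 8 x ULN, bilirubin above 5 x ULN and Hy's Law unchanged. The sponsor's medical lead should confirm that this is what was intended, as 8.5.5 indicates.

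The cost is two words in one table note, carried in a protocol amendment. The sample size, analysis and data collection do not change.
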